 - **time to cardiovascular death or hospitalization for worsening heart failure, whichever occurs first**
 - **time to ischemic fatal or non-fatal stroke or transient ischemic attack, whichever occurs first**
 - **time to the first fatal and non-fatal myocardial infarction**
 - **time to the first fatal and non-fatal stroke**
- **Non-mortality**
 - **time to the first coronary revascularization**
- **Mortality**
 - **time to cardiovascular death**
 - **time to coronary death**
 - **time to death by any cause**

Censoring date

Endpoints are censored differently according to the endpoint categories. The censoring schema are described in below:

- censoring date for the composite and non-mortality endpoints is the EOS date in the OLE study.
- censoring (or time-to-event) for mortality endpoints are detained in appendix C.

Time-to-first-event Definition

- For the time-to-first-event analysis based on combined the parent and OLE data, the events adjudicated as positive in the parent study and occurred prior to or on subject last confirmed survival status date in the parent study (i.e., primary analysis in the parent study; please see the definition in the parent study SAP version 3.1 dated Aug 09, 2016) are included in addition to the events reviewed as positive in the OLE study (defined as below).

For the time-to-first-event analysis based on the OLE data only, mortality events reviewed as positive and occurred prior to or on later of (the EOS date or last known survival status date from eCRF page(s) in this OLE study) and non-mortality events reviewed as positive and occurred prior to or on the EOS date are included. For those subjects who already experience such event in the parent study, their time to event and censor flag are same as those in the parent study.

- For those subjects who didn't experience such event in the parent study, the derivation of the time-to-event and censoring date is presented below

For analyses combined both the parent and OLE studies		
Endpoint	Time-to-event for subjects with events	Censoring date for subjects without events
Composite or Non-mortality	First event onset date reviewed by CEC in OLE study – randomization date in the parent study +1	EOS date in OLE study

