Mortality	Death endpoint date reviewed by CEC in OLE study – randomization date in the parent study +1	For subjects who died not due to death endpoint, the censoring date is the death date (reviewed by CEC) in OLE study For remaining subjects, the censoring date is max (EOS date, last known survival status date from eCRF page(s)) in the OLE study
For analyses based on OLE data only		
Composite or Non-mortality	First event onset date reviewed by CEC in OLE – enrolment date in OLE study +1	EOS date in OLE study
Mortality	Death endpoint date reviewed by CEC in OLE study – enrolment date in OLE study +1	For subjects who died not due to death endpoint, the censoring date is the death date (reviewed by CEC) in OLE study For remaining subjects, the censoring date is max (EOS date, last known survival status date from eCRF page(s)) in the OLE study

Patient-years of follow-up for treatment emergent adverse events

For analyses based on combined both the parent and OLE studies:

- 1) Subjects had first event in parent study: date (first event) – date (first dose date in FOURIER) + 1
- 2) Subjects had first event in OLE: study exposure in parent study + (date (first event) – first dose date in OLE + 1)
- 3) Subjects didn't have events: study exposure in parent study + (min [date (EOS in OLE), date (last dose date in OLE)+30] – first dose date in OLE + 1)

For analyses based on OLE study:

- 1) Subjects had events: date (first event in OLE) – date (first dose date in OLE) + 1

2) Subjects didn't have events: min [date (EOS in OLE), date (last dose date in OLE)+30] – date (first dose date in OLE) + 1

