9.1 General Considerations

Statistical analyses in this open-label study are descriptive in nature. No formal hypothesis will be tested in this study. No statistical inference is planned.

Subject disposition, demographics, and baseline characteristics and exposure to IP will be summarized.

Summary statistics for continuous variables will include the number of subjects (n), mean, standard deviation (SD) or standard error (SE), median, the first (Q1) and third (Q3) quartiles, minimum, and maximum. For categorical variables, the frequency and percentage will be given. The baseline value is defined as the subject's baseline value from the **parent** study as defined in [Section 5.2](#), unless specified otherwise. All analyses will be performed on the OLE safety analysis set.

Interim and final analyses will be based on data collected from this study combined with the data from the FOURIER study as applicable. For all endpoints, results will be summarized by the randomized treatment group from the parent study and overall, unless specified otherwise.

All deaths and cardiovascular events of interest (MI, stroke, coronary revascularization, hospitalization for unstable angina, hospitalization for heart failure, and TIA) will be reviewed by an independent external CEC, using standardized definitions. The CEC is external to Amgen and primarily comprises both academic clinical physicians (to include cardiologists) and medical reviewers trained on the clinical trial protocol, the CEC charter, and CEC processes. The chairman of the CEC is responsible for overseeing the operations in conformance with the CEC charter and for supervising the flow of data between the sponsor/data management and the CEC. Committee members are qualified in the appropriate subspecialty and free of conflict of interest. The CEC reviews events according to pre-specified criteria defined in the CEC charter. The CEC will be blinded to the original randomized treatment group from the **parent** study.

There will be no imputation for missing data other than date imputation described in [Section 8.3.2](#)

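### SAP 5.1 as printed carries FOURIER event times and flags into the OLE-only Kaplan-Meier estimates, because the carry-over sentence is not limited to the combined analysis

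*SAP*

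**What the plan says.** SAP 9.5.3 asks for yearly K-M estimates of events positively reviewed by the Clinical Events Committee (CEC), once for the OLE period and once for FOURIER and OLE combined. SAP 5.1 supplies the derivations, in this order:

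- **Combined analysis.** Positively adjudicated FOURIER events "are included in addition to the events reviewed as positive in the OLE study".
- **OLE-only analysis.** The paragraph begins "For the time-to-first-event analysis based on the OLE data only, mortality events reviewed as positive", sets an upper date limit for deaths, and continues "and non-mortality events reviewed as positive and occurred prior to or on the EOS date are included".
- **Carry-over.** The same paragraph ends with the rule that, for subjects "who already experience such event in the parent study, their time to event and censor flag are same as those in the parent study".
- **Table lead-in.** The next bullet is for subjects who did not "experience such event in the parent study, the derivation of the time-to-event and censoring date is presented below". The table that follows has a combined block, timed from FOURIER randomization, and an OLE-only block. In the OLE-only block the composite and non-mortality event time is "First event onset date reviewed by CEC in OLE – enrolment date in OLE study +1".

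Two rules are stated for all subjects: "censoring date for the composite and non-mortality endpoints is the EOS date in the OLE study" (SAP 5.1) and "All analyses will be performed on the OLE safety analysis set" (SAP 9.1). Protocol 10.4.1 bases the primary analysis of every endpoint, exploratory ones included, on OLE data alone and treats combined analyses as additional.

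**The concern.** A subject with a non-fatal FOURIER event is never sent to the OLE-only row of the table. The only event-time rule printed for that subject is the FOURIER time and flag. A programmer who follows the page would therefore enter a FOURIER event, timed from randomization, into a curve whose other subjects are timed from OLE enrolment. The subject's own first OLE event would be ignored.

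Such an estimate is no longer OLE-only, and it is too high. SAP 9.1 presents results by FOURIER randomized group, so any difference between the groups in FOURIER-period events would also enter curves meant to describe the open-label period.

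**Working it through.** **1. Endpoints affected.** SAP 5.1 lists 10 time-to-first-event endpoints: 6 composite, 1 non-mortality (coronary revascularization) and 3 mortality. Protocol 4.1 requires completion of FOURIER while still on assigned product, so no enrollee carries a FOURIER death and the 3 mortality endpoints are untouched. Non-fatal FOURIER events do not exclude a subject, so 6 + 1 = 7 endpoints are exposed.

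**2. Rules side by side, for a subject with a FOURIER event**

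| Item | Combined analysis | OLE-only analysis as printed |
|---|---|---|
| Events counted | FOURIER and OLE | OLE (inclusion sentence), but FOURIER under the carry-over sentence |
| Event time | FOURIER time from randomization | FOURIER time from randomization; the OLE row excludes this subject |
| Consistent? | Yes | No |

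**3. Direction.** The plan states no K-M figure to reproduce. Let p be the share of enrollees with a FOURIER event, P the longest FOURIER follow-up, and F0 and Fm the OLE cumulative incidence in subjects without and with a FOURIER event. With no dropout and t ≥ P:

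- K-M as printed = p + (1 − p) × F0(t)
- K-M from OLE data only = (1 − p) × F0(t) + p × Fm(t)
- Difference = p × (1 − Fm(t)) = p × S(t), which is never negative

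For t < P the difference is p × (G(t) − Fm(t)), where G(t) is the share of the carried-over events that fall by time t. It is positive whenever those events accrue faster than these subjects' OLE events. That is to be expected, because all of the carried-over events fall within P.

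**4. Size per 1% of enrollees with a FOURIER event (16 of 1600).** With 5-year OLE incidence of 10%, 14% or 20% in these subjects, p × S = 1% × 0.90, 0.86 or 0.80 = 0.90, 0.86 or 0.80 points. At p = 5% it is 4.5, 4.3 or 4.0 points.

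**5. Illustration on assumed rates.** N = 1600 and T = 260 × 7 / 365.25 = 4.98 years come from the plan. Assumed: OLE hazard h = 3% per year, P = 2 years, FOURIER hazard f × h, no dropout. Then p = 1 − exp(−f × h × P), and the OLE-only K-M is 1 − exp(−0.03 × 4.98) = 13.9%, so S = 86.1%.

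| f | p | FOURIER events carried over | p × S (points) | 5-year K-M as printed | First OLE events dropped (N × p × 13.9%) |
|---|---|---|---|---|---|
| 0.5 | 2.96% | 47 | 2.5 | 16.4% | 7 |
| 1.0 | 5.82% | 93 | 5.0 | 18.9% | 13 |
| 1.5 | 8.61% | 138 | 7.4 | 21.3% | 19 |

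**6. Sensitivity.**

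- With 3% per year OLE dropout, simulation gives 16.5, 19.0 and 21.4% against 13.9%.
- If the OLE hazard doubles after a FOURIER event, S = exp(−0.06 × 4.98) = 74.2%, and the excess is 2.2, 4.3 and 6.4 points.
- With p set directly at 5 to 15%, P at 2 to 3 years and OLE hazards of 2 to 4% per year, the excess is about 1.5 to 7 points at 1 year and about 4 to 13 points at 5 years.

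**The case against.** The strongest reply is that the sponsor plainly meant the carry-over for the combined analysis:

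- The sentence is the twin of the next bullet, so a list mark may have been lost and its place in the OLE-only paragraph may mean little.
- The OLE-only inclusion sentence names OLE events only, and the OLE-only rows run from enrolment. A FOURIER event time fits only the randomization origin.
- The patient-years rules for adverse events, in the same section, mention FOURIER events only under the combined analysis.
- Protocol 10.4.1 speaks of the primary analysis, the protocol's exploratory endpoint is subject incidence, and yearly K-M is an SAP addition. Nothing is tested.
- The percentages rest on assumed rates, and the simple p × S result needs no dropout and a time beyond the longest FOURIER follow-up.

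Most of this stands. The intent was probably combined-only, and on that reading the gap is small: event inclusion, censoring date and analysis set are already stated for everyone, and only the table lead-in leaves these subjects without an explicit OLE-only event-time formula. The outputs are exploratory, and the illustrated sizes are not the trial's. But a restored list mark would add no limit. The sentence would then cover both analyses, paired with a bullet whose table also covers both. Likely intent does not change what the page instructs.

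**Conclusion.** The point holds. As printed, SAP 5.1 gives a rule that yields wrong OLE-only K-M estimates for 7 of the 10 time-to-first-event endpoints, against its own OLE-only inclusion sentence and the OLE-only principle in protocol 10.4.1. At 5 years the error is upward, by p × S without dropout, provided FOURIER follow-up was no longer than that. Its actual size cannot be known from the documents; the 2.5 to 7.4 points in the main illustration depend on the assumed hazards and the assumed 2 years of FOURIER follow-up.

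Not affected: the 3 mortality endpoints, the combined analysis, the LDL-C endpoints and the primary adverse event endpoint. Nothing is claimed about crude subject incidence of CEC-positive events, the summary named in SAP Table 9-1. No hypothesis test depends on the affected outputs. It should be fixed, because two programmers could derive different curves from the same page.

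**What to change.** In SAP 5.1:

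1. Limit the carry-over sentence to the combined FOURIER-plus-OLE analysis.
2. Limit the condition in the table lead-in (no such event in FOURIER) to the combined block.
3. State that in OLE-only analyses every subject in the OLE safety analysis set, whatever their FOURIER history, is timed from OLE enrolment to the first CEC-positive OLE event or the OLE censoring date, and that the OLE-only rows apply to all of them.

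This is a wording change to the SAP, with no data or operational cost.

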For each subject, study exposure period in OLE period = [(EOS date – enrollment date) + 1] / 365.25 x 12

Study Exposure Period in Months (For the combined parent and OLE periods)

For each subject, study exposure in combined periods is the sum of the study exposure in the parent study (defined above) plus the study exposure in the OLE period (defined above).

Reflexive Approach for LDL-C and VLDL-C

For all analyses related to LDL-C and VLDL-C, unless specified otherwise, an LDL-C reflexive approach will be used. When calculated LDL-C is less than 40 mg/dL or triglycerides are > 400 mg/dL, the ultracentrifugation (UC) LDL-C value and UC VLDL-C value from the same blood sample will be used instead, if available.

Two Consecutive LDL-C Values < cutoff (25 mg/dL and 40 mg/dL) The algorithm for defining the 2 consecutive LDL-C values < 25 mg/dL / 40 mg/dL separated by at least 21 days within OLE study period is summarized below:

- 1) For each blood sample draw date that has at least one LDL-C value within OLE study period, identify the lowest LDL-C value
 - a. If UC values exist regardless of the presence of calculated LDL-C values, the lowest UC LDL-C value will be used
 - b. If only calculated LDL-C values exist, the lowest calculated LDL-C value will be used
- 2) If a subject has 2 consecutive (separated by at least 21 days) LDL-C values that are < 25 mg/dL / 40 mg/dL within OLE study period, then the subject will be considered as a subject with two consecutive LDL-C values < 25 mg/dL / 40 mg/dL within OLE study period.

Two consecutive LDL-C in the parent study has been defined and derived in the same way as above.

6. Analysis Sets

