6.1 OLE Safety Analysis Set

The OLE safety analysis set includes all subjects who received at least 1 dose of open-label evolocumab in the OLE study.

7. Planned Analyses

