9.3 Important Protocol Deviations

Important Protocol Deviations (IPDs) categories are defined by the study team before the first subject's visit and updated during the IPD reviews throughout the study prior to database lock. These definitions of IPD categories, subcategory codes, and descriptions will be used during the course of the study. Eligibility deviations are defined in the protocol.

The number of subjects reporting Protocol Deviations and Important Protocol Deviations due to COVID-19 impact will be summarized in a table. A Protocol Deviation listing of subjects impacted due to COVID-19 impact will also be provided.

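### Combined parent-plus-OLE rates of death and of adverse events leading to evolocumab withdrawal count parent-study time in which the analysis set rules these events out, so they come out too low

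*SAP*

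**What the plan says.** **Who is analysed.** SAP 6.1: "The OLE safety analysis set includes all subjects who received at least 1 dose of open-label evolocumab in the OLE study". SAP 9.1: "All analyses will be performed on the OLE safety analysis set". SAP 10 records that the set with parent subjects who did not roll over was removed. Protocol 4.1 (criterion 102) requires completion of FOURIER while still on assigned product. Protocol 4.2 (criterion 201) excludes anyone who stopped that product permanently, for any reason.

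**What time is counted in the combined analyses.** In SAP 5.1, time to a mortality endpoint is "Death endpoint date reviewed by CEC in OLE study – randomization date in the parent study +1". Time to a composite or non-mortality endpoint has the same origin: "First event onset date reviewed by CEC in OLE study – randomization date in the parent study +1". The patient-years rule for treatment-emergent adverse events begins "Subjects had first event in OLE: study exposure in parent study" and then adds OLE time to the event; subjects without an event also contribute all their parent exposure. SAP 5.3 says that "study exposure in combined periods is the sum of the study exposure in the parent study" plus that in the OLE.

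**What is reported.** SAP 9.5.1 asks for combined exposure-adjusted rates for a list that includes fatal adverse events and those leading to withdrawal of evolocumab. SAP 9.5.3 asks for exposure-adjusted rates and yearly Kaplan-Meier estimates of events confirmed by the Clinical Events Committee (CEC), for the OLE alone and for the combined periods.

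**What is left open.** SAP 5.1 also says "censoring (or time-to-event) for mortality endpoints are detained in appendix C", and the content of that appendix is not readable in the copy reviewed.

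**The concern.** An exposure-adjusted rate should divide events by time in which they could have been counted. For death, the parent-period numerator is zero by construction: a subject dosed in the OLE was alive at the end of FOURIER. For adverse events leading to permanent withdrawal, it is zero if the eligibility criteria were met. The denominator nevertheless includes the whole parent period and, for mortality, the gap before OLE enrolment as well. This is immortal time.

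The study exists to describe long-term safety, and the combined tables cover the longest observation window in the plan. A reader could take a diluted combined death or withdrawal rate as evidence that risk falls with longer treatment. SAP 10 discloses that only rollover subjects are analysed, but not this consequence.

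**Working it through.** **Plan's own figures.** The documents give no combined rate and no parent person-time, so there is nothing on this point to reproduce. The one design figure, the confidence interval width, does reproduce (at 1%: 2 × 1.96 × √(0.01 × 0.99 / 1600) = 0.975 percentage points), but nothing below depends on it.

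**Inputs**
- OLE length: 260 weeks, about 5 years (Protocol 3.5.1). Four years is used as an assumed case with drop-out.
- Mean parent time P: not given; assumed 1 to 3 years. The only indirect hint is the SAP 4.2 subgroup with at least 7 years of combined exposure: 7 − 260 × 7 / 365.25 = 7 − 4.98 = about 2.0 parent years to qualify.
- Event rate h: not given; assumed constant at 0.5 to 4 per 100 patient-years.

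**Rates.** With OLE length T, mean OLE time at risk is Te = (1 − exp(−hT)) / h. The combined rate under SAP 5.1 is (1 − exp(−hT)) / (P + Te), against a true h, so the fraction lost is P / (P + Te).

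For h = 0.02 and T = 5, Te = (1 − exp(−0.10)) / 0.02 = 4.758 years. With P = 1 the fraction lost is 1 / 5.758 = 17.4%, and 2.00 becomes 1.65 per 100 patient-years. With P = 3 it is 3 / 7.758 = 38.7%, and 2.00 becomes 1.23.

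| OLE years | Rate per 100 PY | Te (years) | Lost, P = 1 | Lost, P = 2 | Lost, P = 3 |
|---|---|---|---|---|---|
| 5 | 0.5 | 4.938 | 16.8% | 28.8% | 37.8% |
| 5 | 2 | 4.758 | 17.4% | 29.6% | 38.7% |
| 5 | 4 | 4.532 | 18.1% | 30.6% | 39.8% |
| 4 | 0.5 | 3.960 | 20.2% | 33.6% | 43.1% |
| 4 | 2 | 3.844 | 20.6% | 34.2% | 43.8% |
| 4 | 4 | 3.696 | 21.3% | 35.1% | 44.8% |

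The assumed event rate hardly matters; the ratio of parent to OLE time decides the size.

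**Mortality Kaplan-Meier.** Take h = 0.02 and parent time spread evenly from a to b years. As written, for t of b or more, survival is exp(−ht) × (exp(bh) − exp(ah)) / ((b − a)h). With delayed entry at OLE enrolment, cumulative mortality is 1 − exp(−h(t − a)). For a = 1.5 and b = 3:

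| Year | As written | Delayed entry | Gap (points) |
|---|---|---|---|
| 3 | 1.49% | 2.96% | 1.47 |
| 5 | 5.35% | 6.76% | 1.41 |
| 7 | 9.06% | 10.42% | 1.36 |

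The as-written curve is flat at zero until the first OLE entries. If parent time is the same for everyone, the two methods agree: with 2 parent years, both give 1 − exp(−0.10) = 9.5% at year 7. A wider spread of 1 to 3 years gives 9.51% against 11.31% at year 7, a gap of 1.80 points. The later distortion thus depends on the spread of parent time and is modest in absolute terms.

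**Denominator for CEC events.** SAP 9.5.3 names none. The two candidates in the SAP, the time-to-event rule in 5.1 and combined study exposure in 5.3, both include parent time.

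**The case against.** **These analyses are supplementary and descriptive.** True. Protocol 10.4.1 makes OLE-only data primary for every endpoint, and no inference is planned. A reader might infer that the primary safety results are biased; they are not. Crude subject-incidence percentages are also unaffected, because no person-time enters them. Both former randomized groups carry the same kind of event-free time, so ratios between them are distorted much less than the rates. The absolute rates by group and overall remain too low.

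**Appendix C may cure it.** It could hold a delayed-entry rule for mortality, and its content cannot be checked here. The table in SAP 5.1 shows no such rule, and an appendix on mortality censoring would not change patient-years for adverse events.

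**Withdrawal events could exist in the parent period.** The set is defined by dosing, and SAP 9.3 foresees breaches of entry criteria ("Eligibility deviations are defined in the protocol"). The statement for withdrawal events therefore holds barring such deviations. For death it needs no such proviso.

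**Fatal adverse events.** A reader might apply the 17% to 45% to the fatal row of the combined adverse event table. That would be wrong. Protocol 10.4.2 and SAP 9.5.1 drop CEC-positive OLE events from that table, and all deaths go to the CEC. The row is low mainly because its numerator has been largely emptied.

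**Composites and non-fatal cardiovascular events.** A reader might infer a similar shortfall here. The documents do not support one: positively adjudicated parent-period events are counted (SAP 5.1), so that time is not event-free. These outputs are conditional on roll-over, since subjects who died or stopped product after a parent event are absent, but the effect cannot be quantified without knowing how roll-over depended on events.

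**Conclusion.** The point holds for combined exposure-adjusted rates of all-cause, cardiovascular and coronary death and, barring eligibility deviations, of adverse events leading to permanent withdrawal of product. The direction follows from the documents. The size, about 17% to 45% too low, rests on the assumed 1 to 3 parent years, 4 to 5 OLE years and a constant event rate. For CEC deaths it also rests on an inferred denominator and on Appendix C containing no delayed-entry rule. The combined mortality curve is too low in the early years. From year 3, at 2 deaths per 100 patient-years, it is low by 0 to about 1.5 points if parent times differ by up to 1.5 years, and by somewhat more if they differ further. This is a correction to supplementary tables and does not challenge the primary analysis.

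**What to change.** - **SAP 5.1, 9.5.1 and 9.5.3:** state that exposure-adjusted rates of the death endpoints and of treatment-emergent adverse events leading to withdrawal of product are reported on OLE person-time only, because membership of the analysis set rules these events out earlier. These OLE-only versions are already planned.
- **Combined mortality Kaplan-Meier, if kept:** let subjects enter the risk set at OLE enrolment and show numbers at risk. If Appendix C already says this, refer to it in 5.1 and 9.5.3.
- **SAP 9.5.3:** name the denominator for CEC event rates.
- **Combined fatal adverse event row:** refer the reader to the CEC death table.
- **All other combined event outputs, including composites:** label them as conditional on completing the parent study on investigational product. The label discloses the selection but does not remove it.

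The cost is SAP wording and relabelling of a few supplementary outputs, with no new data. The downside is that combined death and withdrawal rates are dropped or look less favourable.

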5.3 Other Study Related Definitions

Treatment-emergent adverse event

Events are categorized as Adverse Events (AEs) or **Disease-related Events (DREs)** starting on or after first dose of investigational product as determined by the flag indicating if the event started prior to the first dose on the Events eCRF and up to the EOS/Safety Follow-up visit or 30 days after the last administration of evolocumab, whichever is earlier.

Treatment-Emergent Disease-Related Events

Events categorized as Disease-related Events (DREs) defined in Protocol Section 9.1.1 starting on or after first dose of investigational product as determined by the flag indicating if the disease-related event started prior to the first dose on the Events eCRF and up to the EOS/Safety Follow-up visit or 30 days after the last administration of evolocumab, whichever is earlier.

Analytical Study Week Assignments

Analytical windows will be used to assign parameters to study weeks. The algorithm is provided in [Appendix A](#).

Investigational Product (IP)

Investigational product includes evolocumab 140 mg every two weeks (Q2W) and 420 mg monthly (QM).

IP Exposure Period in Months (Parent study)

For subjects whose last IP dose is Q2W:

IP exposure period = [min(last IP dose date in parent study + 14 days, EOS date) – first IP dose date in parent study + 1] / 365.25 x 12

For subjects whose last IP dose is QM:

IP exposure period = [min(last IP dose date in parent study + 28 days, EOS date) – first IP dose date in parent study + 1] / 365.25 x 12

IP Exposure Period in Months (For OLE period)

For subjects whose last IP dose is Q2W:

IP exposure period in OLE period = [min(last IP dose date in OLE period + 14 days, EOS date) – first IP dose date in OLE period + 1] / 365.25 x 12

For subjects whose last IP dose is QM:

IP exposure period in OLE period = [min(last IP dose date in OLE period + 28 days, EOS date) – first IP dose date in OLE period + 1] / 365.25 x 12

IP Exposure Period in Months (For the combined parent and OLE periods)

For each subject, IP exposure in combined periods is the sum of the IP exposure in the parent study (defined above) plus the IP exposure in the OLE period (defined above).

Study Exposure Period in Months (Parent study)

For each randomized subject, study exposure period = [(EOS date in parent study – Randomization date) + 1] / 365.25 x 12

Study Exposure Period in Months (For OLE period)

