9.5.1 Analyses of Primary Endpoint

The current Medical Dictionary for Regulatory Activities version at the time of data lock will be used to code all adverse events (AEs) and disease related events to a system organ class and a preferred term.

Treatment-emergent adverse events are events with an onset after the administration of the first dose of investigational product as defined in [Section 5.3](#).

The subject incidence and exposure-adjusted subject incidence rate of all treatment-emergent adverse events, serious adverse events, fatal adverse events, adverse events leading to withdrawal of evolocumab, device-related adverse events, and disease-related events will be tabulated by system organ class (SOC), high level term (HLT), and preferred term (PT) in alphabetical order for the overall OLE study period using the OLE safety analysis set. These events will also be presented by yearly subject exposure time intervals. All adverse event summaries for the primary analysis of the primary endpoint will include all treatment-emergent events reported on the Event eCRF, including CEC reviewed events and disease related events.

The analyses described above (subject incidence, exposure-adjusted subject incidence rate) will also be performed combining data from the OLE study and the **parent** study

using the **OLE safety analysis set** and also be analyzed separately for the subgroup of subjects who were randomized to and received evolocumab group in the parent study with ≥ 7 years of the combined exposure for evolocumab across the parent and OLE study. Events from **parent** study classified as Target IP TEAEs will be included (adverse events occurring from the first dose of IP date to 30 days after the last dose of IP date or EOS, whichever occurs first). Disease-related events from the OLE study will be reclassified as adverse events and positively reviewed events from the OLE study will not be included to remain consistent with **parent** study adverse event reporting. This analysis will be presented by the **randomized treatment in the parent study**.

Subject incidence of treatment emergent and serious adverse events occurring in at least 1% of the subjects by preferred term will be provided in descending order of frequency for the overall OLE study period only **and combined parent and OLE study periods**.

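### The combined parent + OLE patient-years rule for treatment-emergent adverse events adds parent exposure in months to OLE time in days, so it understates person-time if applied as written.

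*SAP*

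**What the plan says.** SAP 5.1, under "Patient-years of follow-up for treatment emergent adverse events", gives five rules: three for the combined parent and OLE analysis and two for the OLE-only analysis.

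- **Combined rule 1:** "Subjects had first event in parent study: date (first event) – date (first dose date in FOURIER) + 1".
- **Combined rule 2:** "Subjects had first event in OLE: study exposure in parent study + (date (first event) – first dose date in OLE + 1").
- **Combined rule 3 (no event):** "study exposure in parent study + (min [date (EOS in OLE), date (last dose date in OLE)+30] – first dose date in OLE", plus one day.
- **OLE-only rules:** date differences counted from the first OLE dose.

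None of the five contains a division by 365.25.

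SAP 5.3 defines the parent term used in combined rules 2 and 3, under a heading that gives its unit as months: "For each randomized subject, study exposure period = [(EOS date in parent study – Randomization date) + 1] / 365.25 x 12". The next definitions in that section reuse the term and point back to this one: "For each subject, study exposure in combined periods is the sum of the study exposure in the parent study (defined above").

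SAP 9.5.1 says which parent events count in the combined numerator: "adverse events occurring from the first dose of IP date to 30 days after the last dose of IP date", or to end of study if that is earlier. The combined rates are also to be produced for the subgroup randomized to and treated with evolocumab in the parent study with at least 7 years of combined exposure.

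**The concern.** Combined rules 2 and 3 add a number of months to a number of days. Two years of parent follow-up enter the sum as 24 rather than as about 730, so most of the parent person-time disappears. The denominator is too small and the rate too high.

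The error is not a constant factor. Rule 1 subjects contain no mixed sum, and among rule 2 subjects the relative loss depends on when the first OLE event occurs. Inflation therefore differs between frequent and infrequent event types, and no single scaling would put it right afterwards.

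There is also a smaller inconsistency of window. Rule 1 starts at first parent dose. Rules 2 and 3 take parent time from randomization to parent end of study. The parent numerator runs from first dose to the earlier of 30 days after last dose and end of study. Rule 3 truncates OLE time in that way but not parent time.

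At stake are the exposure-adjusted adverse event rates over the longest exposure the programme offers, tabulated by system organ class, high level term and preferred term.

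**Working it through.** The documents give no patient-years total or combined rate, so there is no stated figure to reproduce. The check applies the rules literally and compares the result with the same rules in one unit.

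**Inputs**
- Parent study exposure in months, *m*: formula in SAP 5.3. Parent duration per subject is not stated; I assume 2 to 3 years (*m* = 24 to 36). With an OLE of about 5 years, membership of the 7-year subgroup implies about 2 parent years or more.
- OLE time in days, *d*: 260 weeks × 7 = 1820 for an event-free completer. The cohort check uses 1821, the week 260 visit day in SAP Appendix A; the difference is immaterial.
- The step from days to years (divide by 365.25) is mine, because SAP 5.1 does not write it.

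**Single subjects**

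Literal: (*m* + *d*) / 365.25. One unit: *m* / 12 + *d* / 365.25.

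| Case | *m* | Literal PY | One-unit PY | Shortfall |
|---|---|---|---|---|
| Event-free, *d* = 1820 | 24 | (24 + 1820)/365.25 = 5.05 | 2 + 4.98 = 6.98 | 27.7% |
| | 30 | 5.07 | 7.48 | 32.3% |
| | 36 | 5.08 | 7.98 | 36.3% |
| First event at OLE day 365 | 24 | (24 + 365)/365.25 = 1.07 | 3.00 | 64.5% |
| | 36 | 1.10 | 4.00 | 72.5% |

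**Cohort rates**

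A rate pools all three rules, so single-subject ratios are not rate ratios. Assume a constant first-event hazard λ per year, parent duration *P* years, OLE duration *O* = 1821/365.25 = 4.986 years, and no dropout. Per subject:

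- true expected person-time: T = (1 − exp(−λ(P + O))) / λ
- person-time lost, only by subjects who reach the OLE event-free: S = P × (1 − 12/365.25) × exp(−λP)
- rate inflation: T / (T − S)

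Example, λ = 0.02 and P = 2: T = 6.520, S = 1.858, inflation = 6.520 / 4.662 = 1.40. A true rate of 2.0 per 100 PY would be shown as 2.8.

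| True rate per 100 PY | P = 2 | P = 2.5 | P = 3 |
|---|---|---|---|
| 0.5 | 1.39 | 1.48 | 1.58 |
| 2 | 1.40 | 1.49 | 1.59 |
| 5 | 1.42 | 1.52 | 1.61 |
| 20 | 1.53 | 1.61 | 1.67 |
| 50 | 1.58 | 1.55 | 1.49 |
| 100 | 1.36 | 1.25 | 1.17 |

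A simulation of 400,000 subjects per cell agrees with this table to within 0.01. Inflation falls again for very common events because most first events then occur in the parent study, under rule 1.

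**Internal check on the 7-year subgroup**

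An event-free subject with 36 parent months, followed to OLE day 1851 (the EOS day in SAP Appendix A), is credited with (36 + 1851)/365.25 = 5.17 patient-years. The subgroup is selected for at least 7 years of exposure.

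**Window mismatch, once units are fixed**

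Extra parent days outside the event window, as a share of an event-free completer's denominator (parent 2 to 3 years):
- 7 days: about 0.3%
- 30 days: 1.0% to 1.2%, for example 30 / (730.5 + 1821) = 1.2%
- 90 days: 3.1% to 3.5%

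This lowers the rate, opposite to the unit error. It is likely to be small here, because protocol inclusion criterion 102 and exclusion criterion 201 admit only subjects who finished the parent study still on investigational product.

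**The case against.** The best reply is that SAP 5.1 leaves the conversion to years unstated in all five rules. A programmer must supply one anyway, and the months label in SAP 5.3 is explicit. On that view the plan merely omits a conversion, and my literal figure combines a division that the SAP does not write with a conversion that I decline to make. Verification of output under SAP 8.7 would also be expected to catch a 7-year subject showing about 5 patient-years.

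Part of this stands. The numbers depend on the added division and on an assumed parent duration, and a programmer may well convert silently. But the two cases differ. Rule 1 and the OLE-only rules are valid in days and need only one common divisor. No single divisor makes the sum in rules 2 and 3 valid. SAP 5.3 also writes its conversions out, so the omission is not a convention of the document. A programmer or validator who follows the text reproduces the error.

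Three stronger readings are tempting and not supported:

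- **That the primary analysis is wrong.** Protocol 10.4.1 and 10.4.2 base it on OLE data only, and the OLE-only rules do not mix units.
- **That every combined exposure-adjusted rate is affected.** SAP 9.5.3 also plans combined rates for events positively reviewed by the Clinical Events Committee, but this rule is headed for treatment-emergent adverse events only.
- **That rates could double or triple.** Person-time for one subject with an early OLE event can be out by that much; no cohort rate in the table is inflated by more than 1.67.

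Adding the two periods as separate blocks was a deliberate change in SAP version 3.0, and that intent is not in question.

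**Conclusion.** Combined rules 2 and 3 are wrong as written: they sum incompatible units, and no other part of the SAP repairs this. Under a parent duration of 2 to 3 years, a constant hazard and complete OLE follow-up, literal application inflates combined adverse event rates about 1.4 to 1.6 times for events at 0.5 to 5 per 100 patient-years, and about 1.2 to 1.7 times for events at 20 to 100. The same rule serves the 7-year exposure subgroup. The size rests on those assumptions; the direction does not.

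The window mismatch is real but secondary.

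A reader might infer that reported combined rates are wrong. The documents cannot show that; they show only that the written specification is. Because the combined analysis is additional to the primary one and all analyses are descriptive, this is a point that should be fixed rather than one that undermines the study.

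**What to change.** In SAP 5.1, combined rules 2 and 3, replace the parent study exposure term with:

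min(parent EOS date, parent last IP dose date + 30) − parent first IP dose date + 1, in days.

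Then state once that the total in days is divided by 365.25 under all five rules, including combined rule 1 and the two OLE-only rules. If only rules 2 and 3 were converted, rule 1 would stay in days.

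This settles the unit, the starting point and the end of the window together. It matches the numerator in SAP 9.5.1 and keeps the two periods as separate blocks.

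The cost is one corrected definition and a small program change, with no new data. If combined rates have already been produced, check the program first: an event-free subject in the 7-year subgroup should show about 7 patient-years or more, not about 5.
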